Formulation	Sprays	Formulations	Sprays
CTY-5339-A	1	CTY-5339-CB	1
CTY-5339-A	2	CTY-5339-CB	1
CTY-5339-CB	1	CTY-5339-A	1
CTY-5339-CB	1	CTY-5339-A	2

To maintain double-blind conditions, the CTY-5339-CB subjects in the two spray sequences will also receive one spray with the vehicle control (CTY-5339-P). A third party not involved with evaluating subjects will administer the drug. The CTY-5339-P Vehicle will be sprayed outside the circumscribed area to avoid dilution of active drug. Efficacy evaluations will be done at 1-5 minute intervals beginning immediately after drug administration and will include:

Pin Prick (PPT) & QST Heat Sensation Tests:

For PPT, evaluations will be done at 1 minute intervals for the first 5 minutes to capture onset of anesthesia. Starting at 5 minutes after drug administration, both PPT and QST will be done at 5 minute intervals up to the one hour time point. If there is no indication of anesthesia by 10 minutes, the subject will be considered a treatment failure and the assessment of PPT and/or QST, as appropriate, will be discontinued. In addition, once onset of anesthesia has occurred, if there is no longer any anesthesia at two consecutive evaluation time points from 10 minutes onward, the assessment of PPT and/or QST, as appropriate, will be discontinued.

STUDY

Pin Prick Test (PPT): The PPT will be assessed, using a 90-mm, 26-

DESIGN: (cont) 1 gauge pencil-point spinal needle (Polymedic; Temena S.A., Bondy, France or equivalent). At screening, 3 pin pricks will be performed on each cheek. Pin pricks will be assessed using a 0 (no pain) to 10 (severe pain) Numerical Rating Scale (NRS). In order to be eligible for the study, for each cheek, subjects must have a minimum score of "3" for the last 2 pin pricks, and one of those scores has to be "4" or higher.

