8.4 Hypothesis

The following hypotheses will be tested to analyze the primary outcomes of the study:

- The null hypothesis that the duration of anesthesia (PPT and QST Heat) for the one spray CTY-5339-A group is the same as the corresponding duration for the CTY-5339-CB one spray group will be tested against the alternative hypothesis that the means are not equal.

The following hypotheses will be tested to analyze the secondary outcomes of the study:

- The null hypothesis that the duration of anesthesia (PPT and QST Heat) for the two spray CTY-5339-A group is the same as the corresponding duration for the CTY-5339-CB one spray plus CTY-5339-P one spray group will be tested against the alternative hypothesis that the means are not equal.
- The null hypothesis that the onset of anesthesia (PPT and QST Heat) for the CTY-5339-A groups is equal to the corresponding onset for CTY-5339-CB group will be tested against the alternative hypothesis that the means are not equal.
- The null hypothesis that the onset time until the first responder event (PPT and QST Heat) for the CTY-5339-A groups is equal to the corresponding onset time until a first responder event for CTY-5339-CB group will be tested against the alternative hypothesis that the event times are not equal.
- The null hypothesis that the duration time until the first non-responder event (QST and PPT) for the CTY-5339-A groups is equal to the corresponding duration time until the first non-responder event for CTY-5339-CB group will be tested against the alternative hypothesis that the event times are not equal.

The predicted outcome is that CTY-5339-A when locally applied to cheek mucosal tissue in the mouth will have an onset comparable to the fastest constituent, benzocaine, and a prolonged effect comparable to the longest acting constituent, tetracaine, of the combination product. The study also is designed to demonstrate that both the CTY-5339-A one and two-spray dosages are safe. (The assumption is made that benzocaine has a faster onset of action than tetracaine HCl.)

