9. SUMMARY OF STUDY DESIGN

This is a single-dose, double-blind and single-center study with an active control treatment. All subjects will remain at the study center for each of the two 60 minute test sessions. The volunteer subjects will be tested at two different test sessions separated by 4-14 days and serve as their own control.

The study will include 76 subjects with 60-minute evaluations at each test session.

At each session, a circular area of approximately 1 inch in diameter will be isolated on one side of the cheek. Each session will use a different side of the cheek. The possible sequences of treatments at the two sessions are:

Session 1		Session 2	
Formulation	Sprays	Formulations	Sprays
CTY-5339-A	1	CTY-5339-CB	1
CTY-5339-A	2	CTY-5339-CB	1
CTY-5339-CB	1	CTY-5339-A	1
CTY-5339-CB	1	CTY-5339-A	2

(To maintain double-blind conditions, the CTY-5339-CB subjects in two spray sequences will also receive one spray with the vehicle control (CTY-5339-P) just outside the circumscribed area. A third party not involved with evaluating subjects will administer the drug.)

For PPT, evaluations will be done at 1-minute intervals following drug administration for the first 5 minutes to capture onset of anesthesia. Starting at 5 minutes after drug administration, both PPT and QST will be done at 5-minute intervals up to the one hour time point. Once onset has occurred, if there is no analgesia at two consecutive evaluation time points (from 10 minutes onward), the session will be discontinued. In addition, if onset of analgesia has not occurred by 10 minutes post dose, the subject will be considered a treatment failure and no further assessments will be made.

PPT: The PPT will be assessed, using a 90-mm, 26-gauge pencil-point spinal needle (Polymedic or equivalent; Temena S.A., Bondy, France or its equivalent). At each post dosing time point, PPT will be assessed in 3 repetitions on the non-treated site using a 0-10 Numerical Rating Scale (NRS) with "0" as no pain and "10" as severe pain. PPT will then be assessed in 3 repetitions on the treated site. These assessments will be compared to the contra-lateral, non-treated site as "No pain", "Less Pain" or "Similar/More Pain". "No Pain" or "Less Pain" at an application site will be recorded as presence of analgesia/anesthesia ("Responder").

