QST: The heat stimuli are delivered in 3 repetitions, with inter-stimulus intervals of 30s. The basal thermode temperature is set at a comfortable 35°C. The rate at which the thermode heats up is set at 0.5°C/s, while the rate at which it cools down is set at 8°C/s. The maximum thermode temperature is set at 51°C. The first stimulus is disregarded and the remaining two stimuli are averaged for data analysis. In situations where a maximal analgesia/anesthesia effect is demonstrated in the initial two repetitions, the QST test will not be repeated for the third repetition and the data will be recorded as maximal effect (51°C) based on the first two repetitions.

Heat sensation threshold will be defined as the temperature at which the subjects first start to feel tingling, warmth, heat, or pain. All tests will be done near the center of the circumscribed area, but in a different place at each evaluation time point. For QST, the first time point after Baseline will begin at 5 minutes after drug administration. Subjects will have a hand held mouse that turns off the heat probe when they first start to feel tingling, warmth, heat, or pain. At the maximum heat level of 51° C, the heat probe turns off automatically. With a brief exposure at 51° C, there is no damage to the mucosal tissue.²⁵

Randomization: A randomization code will determine in which circumscribed area each treatment is administered (left or right cheek). Immediately prior to beginning each 60 minute test session, both the contra-lateral cheek and the cheek to be dosed will be evaluated with the PPT. For QST, the screening assessments will be performed on both cheeks, while during each treatment Session, at Baseline and all post-dosing time points, assessments will be performed on the treated cheek only.

Subjects retain the right to withdraw from the study at any time.

The PPT and QST tests will be done near the center of each evaluation area but in a different place at each evaluation time point. For PPT, the non-treated control cheek will always be tested before the treated area. The testing will be done in the following order where applicable: PPT and then QST.

A safety phone follow-up call will occur 3 days (± 1 day) after the Session 1 and 15 days (± 2 days) following Session 2.

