13.4 Data Adjustments and Derived Endpoints

13.4.1 Time Windows

Because some subjects may complete their assessments at times differing from the scheduled times, each such score will be adjusted so as to reflect more accurately the score that would have been observed had it been recorded at the scheduled time. With the exception of the 1-5 minute PPT evaluations, time windows will be created for each of the 5-minute scheduled PPT time points, the widths being ± 3 minutes. The time window for the 1-5 minute PPT evaluations will be ± 30 seconds.

- If an assessment is performed within a time point window, the corresponding value will be assigned to that time point (*e.g.*, an assessment performed anywhere between 3 and 7 minutes from the previous evaluation, regardless of when it was scheduled, will be assigned to the scheduled 5 minute time point).

If a particular time point has no value within its window, then the PPT or QST Heat value will be assigned using either Last Observation Carried Forward (LOCF) or Next Observation Carried Backward (NOCB). In particular, LOCF will be used for missing data prior to onset, and NOCB will be used for missing data after onset to conservatively estimate both onset and duration.

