13.5 Statistical Methods for Efficacy Evaluations

The primary efficacy analyses will be based on Modified Intent-to-Treat Population. The key comparisons will include:

1. CTY-5339-A, one spray versus CTY-5339-CB, one spray

The co-primary efficacy variables are duration of effect as measured by PPT and QST Heat. Duration of effect is defined as the time (in minutes) from onset to treatment failure (*i.e.*, for PPT, an assessment of “Same/More” pain, and for QST, the average heat temperature is greater than the average heat temperature at Baseline (non-treated cheek), up to the 60-minute time point (at two consecutive time points). For those discontinuing from the study for any other reason, the time to treatment failure will be censored at the last assessment time.

The secondary efficacy variables include:

- Duration of effect (PPT and QST) for CTY-5339A two sprays versus CTY-5339-CB, one spray plus CTY-5339-P one spray

- Duration of effect (PPT and QST) for CTY-5339A two sprays versus CTY-5339-A one spray
- Onset of anesthesia in minutes for PPT and QST Heat
- Percentage of responders at each time point for PPT and QST Heat for both onset and duration

Continuous variables will be analyzed via an ANOVA model with treatment effects at each of assessed time points. Pairwise comparisons for variables related to percentages will be analyzed via chi square tests. The 95% confidence intervals of the treatment differences will be presented using normal approximation with continuity correction, if appropriate. Pairwise comparisons for time-to-event related variables will be analyzed via a log rank model with treatment effects. Median time to event will be estimated and the 95% confidence intervals for the median will be presented, if appropriate.

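### Read test by test, QST onset can only be 5 minutes, 10 minutes or failure, so an onset time in minutes is too late and cannot separate products that both act within 5 minutes

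*Combined protocol and SAP*

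**What the plan says.** **QST schedule.** Section 9: "For QST, the first time point after Baseline will begin at 5 minutes after drug administration". The grid is then: "Starting at 5 minutes after drug administration, both PPT and QST will be done at 5-minute intervals up to the one hour time point". The flow chart in section 4 agrees, with PPT alone at 1 to 4 minutes.

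**Upper limit on onset.** Section 9: "if onset of analgesia has not occurred by 10 minutes post dose, the subject will be considered a treatment failure". It adds that nothing further is assessed. The synopsis (section 3) applies the same limit by test: "the assessment of PPT and/or QST, as appropriate, will be discontinued".

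**PPT schedule.** Section 9, for PPT: "evaluations will be done at 1-minute intervals following drug administration for the first 5 minutes to capture onset of anesthesia".

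**How time is recorded.** Section 8.4 describes onset time as running to the first responder event. Section 13.4.1: "If an assessment is performed within a time point window, the corresponding value will be assigned to that time point". The windows there are written for PPT; QST is named only in the rule for missing values.

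**Planned analysis.** Section 13.5 lists as a secondary variable: "Onset of anesthesia in minutes for PPT and QST Heat". Section 8.4 begins one of its secondary hypotheses: "The null hypothesis that the onset of anesthesia (PPT and QST Heat) for the CTY-5339-A groups is equal". The alternative there is unequal means, and a further hypothesis tests unequal event times. Section 13.5 assigns ANOVA to continuous variables, and log-rank tests and medians to times to event. Interval censoring is not mentioned.

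**Prediction.** Sections 3 and 8.4 predict an onset comparable to that of benzocaine. No margin is given.

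**The concern.** Onset is one of the two things the study sets out to evaluate (section 8.2). The minute-by-minute PPT readings show that the protocol regards the first 5 minutes as the interval in which onset needs to be captured. QST has no reading inside that interval, yet the plan treats QST onset as a time in minutes, with means, medians and tests of difference.

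Two things are at stake. First, a reported QST onset of 5 minutes may be the first scheduled reading and not the time at which the drug acted. Second, if both products act before 5 minutes, both are recorded at 5. The schedule alone then produces the predicted result, and the absence of a difference may be taken as evidence for it. An equivalence margin would not cure this, because the variable cannot show a difference inside the interval.

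**Working it through.** The documents give no onset distribution, effect size or power (section 13.1), so there is no figure to reproduce. The exposure count is consistent: 76 × 2 = 152 = 38 + 38 + 76, which gives 38 versus 38 exposures for each paired comparison.

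**Step 1. Possible values.** The readings are at 5, 10, 15 … 60 minutes, and the latest admissible onset is 10 minutes. Judged per test, QST onset is therefore 5, 10 or failure.

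**Step 2. Pairs of onset times t and 2t, each moved up to the next reading.**

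| True onset (min) | QST record | PPT record |
|---|---|---|
| 1 vs 2 | 5 vs 5 | 1 vs 2 |
| 2 vs 4 | 5 vs 5 | 2 vs 4 |
| 2.5 vs 5 | 5 vs 5 | 3 vs 5 |
| 3 vs 6 | 5 vs 10 | 3 vs 10 |
| 5 vs 10 | 5 vs 10 | 5 vs 10 |
| 6 vs 12 | 10 vs failure | 10 vs failure |

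A doubling disappears on QST when 2t ≤ 5, that is t ≤ 2.5 minutes.

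**Step 3. Size of the distortion.** Assume lognormal onset with log SD 0.5. The true mean is median × exp(0.5²/2) = median × 1.133. The recorded mean is 5 + 5 × P(onset > 5), with P(onset > 5) = 1 − Φ(ln(5/median)/0.5). This scores any onset after 5 minutes as 10.

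- Medians 1 vs 2: P(onset > 5) = 0.0006 and 0.0334, so 99.9% and 96.7% are recorded at 5. Recorded means are 5.00 and 5.17; true means are 1.13 and 2.27. The difference of 1.13 is recorded as 5 × (0.0334 − 0.0006) = 0.16.
- Medians 1.5 vs 3: P = 0.0080 and 0.1535. The difference of 1.70 is recorded as 5 × 0.1455 = 0.73.
- Medians 2 vs 4: P = 0.0334 and 0.3277. The difference of 2.27 is recorded as 5 × 0.2943 = 1.47.

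**Step 4. Would the planned test still detect a doubling?** Simulation of 38 versus 38, two-sided log-rank at 0.05, 1,500 runs per cell. Assumptions: lognormal onset, failures censored at 10 minutes, error-free classification, and the two sessions treated as independent. Power at log SD 0.3 / 0.5 / 0.8:

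| Medians (min) | QST | PPT |
|---|---|---|
| 1 vs 2 | 0.00 / 0.04 / 0.44 | 1.00 / 1.00 / 0.92 |
| 1.5 vs 3 | 0.09 / 0.76 / 0.69 | 1.00 / 1.00 / 0.92 |
| 2 vs 4 | 0.98 / 0.97 / 0.78 | 1.00 / 1.00 / 0.93 |
| 3 vs 6 | 1.00 / 1.00 / 0.87 | 1.00 / 1.00 / 0.92 |
| 5 vs 10 | 1.00 / 1.00 / 0.90 | 1.00 / 1.00 / 0.92 |

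Step 2 concerns single pairs of times; step 4 concerns groups. With medians of 2 and 4 minutes, QST sees the doubling only because the slower product's upper tail passes 5 minutes. When nearly all onsets fall before 5 minutes, as with 1 vs 2, there is almost nothing to detect.

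**Step 5. Dependence on the 10-minute rule.** If PPT onset alone kept a subject in QST testing, a QST onset of 15 minutes or later could be recorded. The floor at 5 minutes is the same on either reading.

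**The case against.** A reader might infer that QST will show comparable onset whenever one product is twice as slow. The documents do not support this. They give no onset times, and step 4 shows that a doubling is usually detected once median onsets reach about 2 versus 4 minutes. Those power figures are somewhat favourable, because Appendix 2 counts any average above Baseline as a response. If half of the subjects without effect responded by chance at each reading (an assumption), power for 2 vs 4 minutes would fall to about 0.64 / 0.71 / 0.43. That weakens the reassurance but does not make the stronger claim true.

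A reader might also infer that the trial cannot measure early onset at all. It can: the 1-minute PPT readings cover the interval, and PPT onset is a parallel secondary variable with high simulated power in the same scenarios.

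It is also fair to say that section 8.3.2 already lists responder percentages by time point for QST, that the synopsis plans to compare the percentage with onset, that the formal onset tests are of difference, and that no rule turns non-significance into a claim of equivalence. All of this limits the consequence. None of it corrects the QST analysis in minutes, which stays in sections 8.4 and 13.5 beside the prediction of comparable onset.

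**Conclusion.** The point holds as a limit on a secondary endpoint. Judged per test, QST onset has two recordable times plus failure. Every onset before 5 minutes is entered as 5, so means and medians in minutes are too late, and products that both act within 5 minutes cannot be separated.

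How much this matters depends on onset times that the documents do not give. In the assumed scenarios, power to see a doubling on QST runs from about zero (medians 1 vs 2 minutes, log SD 0.3) to near certainty (3 vs 6 minutes, log SD 0.3 or 0.5). The figures rest on lognormal onset, censoring of failures at 10 minutes (the plan does not say how failures enter the onset analysis), error-free classification and independent sessions.

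A non-significant QST onset result should therefore not be cited as support for comparable onset. The argument does not touch the co-primary comparison of duration.

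**What to change.** 1. In sections 8.3.2, 8.4 and 13.5, base onset-time estimates and any conclusion about onset on PPT.
2. For QST, report and compare the percentages with onset at 5 minutes, with onset at 10 minutes, and with failure. The responder percentages by time point are already planned. The onset categories need a line of their own, because a responder at 10 minutes may have had onset at 5.
3. If a QST onset time is kept, analyse it as interval-censored (0–5 minutes, 5–10 minutes, failure), state how failures are handled, and say that differences within the first 5 minutes cannot be seen.
4. Reconcile the synopsis and section 9 on whether failure by 10 minutes is judged separately for PPT and QST.

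Adding 1-minute QST readings is not a practical alternative. Three stimuli with two 30-second gaps use 60 seconds before any heating time. Even when the third stimulus is skipped because the first two reach 51°C, heating at 0.5°C/s from 35°C takes 32 seconds each, so the assessment lasts 32 + 30 + 32 = 94 seconds.

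The cost is wording only, with no added testing. One nominal secondary onset-time endpoint is lost for QST.

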9.1 Number of Subjects

The study will include 76 completed subjects. It is anticipated that up to 150 ASA Category I and II subjects will be screened to obtain the 76 subjects needed for the study.

9.2 Inclusion Criteria

Individuals may be included in the study provided they meet all of the following inclusion criteria:

- a. Male and female subjects between 18-75 years of age with a Body Mass Index (BMI) ≤ 32 ;
- b. Subjects are ASA Category I or II and are in normal physical health as judged by physical and laboratory examinations;

- c. Subjects with normal appearance of the oral mucosal tissues;
- d. At screening and at Baseline during Session 1, subjects with PPT scores on both cheeks of at least “3” (on a 10 point NRS) on the last 2 of 3 readings, 1 of which must be a score of at least “4”;
- e. Subjects with mean QST Heat sensation temperature assessments on both cheeks of 48.5°C or less based on the average of the last 2 of the 3 readings at screening or with a mean QST Heat sensation temperature assessment of 48.5°C or less based on the average of the last 2 of the 3 readings on the treated cheek at Baseline during Session 1;
- f. Subjects must agree to refrain from ingesting any systemic or topical analgesic medication for 3 days or 5 half-lives of the drug prior to and during each study session and alcohol for 1 day prior to and during each study session;
- g. Subjects must agree to refrain from using mouth rinses, cough drops or throat lozenges on the day of each test session;
- h. Female subjects must be physically incapable of childbearing potential (postmenopausal for more than 1 year or surgically sterile) or practicing an acceptable method of contraception (hormonal, barrier with spermicide, intrauterine device, vasectomized or same sex partner, or abstinence). Subjects using hormonal birth control must have been on a stable dose of treatment for at least 30 days and received at least 1 cycle of treatment prior to randomization. At Screening and at Baseline of both sessions, all females of childbearing potential must have a negative urine pregnancy test and not be breastfeeding;
- i. Negative urine drug screen for drugs of abuse at Screening and at Baseline for each treatment session. A positive drug screen result may be permitted if the subject has been on a stable dose of an allowed medication for >30 days;
- j. The subject is capable reading, comprehending, and signing the informed consent form.

9.3 Exclusion Criteria

Individuals are not eligible for participation in the study if any of the following are noted:

- a. Subjects with a history of any significant hepatic, renal, endocrine, cardiac, neurological, psychiatric, gastrointestinal, pulmonary, hematologic, or metabolic disorders, including glaucoma, diabetes, emphysema, and chronic bronchitis;
- b. Subjects with a history of any type of cancer other than skin related cancers;
- c. Subjects with conditions that affect the absorption, metabolism, or passage of drugs out of the body, (e.g., sprue, celiac disease, Crohn’s disease, colitis, or liver, kidney, or thyroid conditions);

- d. Subjects with any history of alcohol or substance abuse (including a positive drug screen test);
- e. Subjects that currently have or have a history of uncontrolled hypertension;
- f. Subjects with a known hypersensitivity to any local anesthetic drug;
- g. Subjects with a hematocrit level significantly below the normal range on the screening laboratory examination (as judged by the PI) or a pulse oximetry reading of less than 96% at screening or at Baseline of either session;
- h. Subjects with any clinically significant abnormal lab result (as judged by the PI);
- i. Subjects with any condition or history felt by the Investigator to place the subject at increased risk;
- j. Subjects who have smoked or chewed tobacco-containing substances within 6 months prior to the start of the study;
- k. Subjects judged by the Investigator to be unable or unwilling to comply with the requirements of the protocol;
- l. Subjects who have used an investigational drug within 30 days prior to entering the study;
- m. Subjects who have donated blood within 3 months prior to the start of the study;
- n. Subjects who have previously participated in the trial;
- o. Subjects who are members of the study site staff directly involved with the study or a relative of the Sponsor or other personnel involved with the study.

